**- The effect of per oral immunotherapy treatment in severe IgE mediated milk, peanut and egg allergy in adults.**

***Summary***

Prospective study on per oral immunotherapy treatment in IgE mediated milk, peanut or egg allergy in adults ( $\geq 18$  year olds).

***1. Background***

In Finland, the estimated prevalence of physician-diagnosed food allergy in 1-4 year old children is 9%, and the most common allergen is milk (Pyrhönen K 2009). The overall food allergy has been reported to be 3.7% (Sicherer SH 2006). Hen's egg allergy is among the most common food allergies in childhood. In addition, it predicts later development of allergic disease such as asthma. Most of the egg and milk allergy is transient and disappears in childhood. Currently, the standard of care for food allergy includes strict allergen avoidance. However, oral immunotherapy (OIT) has been under investigation in children milk, egg, and wheat allergy. Previously, induction of clinical egg tolerance has been reported with egg oral immunotherapy in children aged from 3 to 13 years (Vickery BP 2010). In adults, strict avoidance is still the standard care but there is also growing interest in treatment of severe food allergy with oral immunotherapy or anti-IgE (Sicherer SH 2006, Sicherer SH 2010).

In respiratory allergy, the administration of allergen immunotherapy is known to alter the natural history of allergic disease and to induce tolerance against allergens (Durham SR 1999). Oral immunotherapy has been introduced also into treatment of allergic rhinitis with good results. However, there is very little information on oral immunotherapy in severe food allergy in adults and no information on the effect of oral immunotherapy on asthma in adults.

In the study of Buchanan et al., 7 subjects were enrolled into egg oral immunotherapy study (Buchanan AD 2007). All the study subjects (mean age 3.7 years) completed the study. All the study subjects had atopic dermatitis and 43% had asthma. All patients had history of egg-ingestion reactions but none had a history of anaphylaxis to egg. Cumulative egg dose at first treatment varied between 17.6-1012 mg and the initial daily home dose varied

between 25-200 mg. Mean baseline egg-specific IgE-level in the study was 24 kU/L (SD 44 kU/L) and 24-month level 12 kU/L (SD 19 kU/L).

In the study of Vickery et al., 8 patients were enrolled into egg oral immunotherapy study (Vickery BP) (median age 5 years). Of these, 75% had atopic dermatitis and 38% asthma. 6 of these 8 patients completed the study. 83% of these six patients developed allergic symptoms during the initial dose escalation day, and 50% developed allergic symptoms during the build-up phase. The mean baseline egg-white specific IgE level was 25 kU/L.

Allergen components Ara h2 and Ara h6 have been estimated to be the best predictive components for symptomatic peanut allergy. In studies on adults, the threshold for allergic symptoms in the challenge tests pre-OIT have varied from 5-50 mg or from 6-100 mg. In the study of Syed et al. symptom threshold in four adult patients (18- 45 years) before OIT were 6mg (peanut specific IgE 20.9 kU/l), 25mg (peanut specific IgE 20.6 kU/l), 100mg (peanut specific IgE 264 kU/l), 50mg (peanut specific IgE 149 kU/l).

In a Cochrane review on egg allergy it was agreed that OIT can desensitize a large number of egg-allergic patients but the long-term tolerance was unknown. However, sustained unresponsiveness in food allergy has been reported to increase by longer duration of immunotherapy in egg allergy. In a study with 5-18 year old children, sustained unresponsiveness increased from 27.5% (immunotherapy for two years) to 50.0% when OIT was continued for four years.

In the same Cochrane review side effects were brought into discussion since sixty nine per cent of the participants presented with mild-to-severe adverse effects during OIT. Five of the 100 participants required epinephrine. This safety issue has been further studied in peanut allergy OIT, where 352 treated patients received 240 351 doses of peanut and experienced 95 reactions that were treated with epinephrine. Only three patients received two doses of epinephrine and none required more intensive treatment. A total of 298 patients achieved the maintenance dose (thus with a success rate of 85%). In addition to OIT also sublingual immunotherapy has been studied in peanut allergy. OIT was reported to be far more effective than sublingual therapy but also with more adverse reactions.

In milk allergy, accordingly, OIT was more effective than sublingual therapy but also with more adverse reactions. Only one of the 10 patients receiving sublingual therapy passed the milk challenge after immunotherapy. With oral immunotherapy six out of ten (sublingual therapy first and then continued with oral immunotherapy) and eight out of ten passed the milk challenge after OIT. In a Cochrane review on OIT for milk allergy, the conclusions were similar to peanut allergy. OIT is effective but is associated with side effects and long-term tolerance has not been established.

This is the second part of the oral immunotherapy study in adults at Skin and Allergy Hospital. The preliminary results for oral immunotherapy since 2012 are presented in the paragraph 4.

### **3. Study plan**

#### **3.1. Subjects**

We study 100 subjects. All subjects are adults having no other severe chronic diseases.

- (a) **30** patients (  $\geq 18$  year olds) that have IgE mediated severe milk allergy
- (b) **30** patients (  $\geq 18$  year olds) that have IgE mediated severe peanut allergy
- (c) **30** patients (  $\geq 18$  year olds) that have IgE mediated severe egg allergy
- (d) up to **10** patients whose oral immunotherapy against milk allergy has started as individually given treatment for clinical need

The diagnosis of milk allergy is verified with positive history, skin prick test ( $>5$  mm), egg and milk allergen specific IgE antibodies ( $>5.0$  kU/l). In addition, food allergy is verified with an open label (milk allergy) or blind (peanut and egg allergy) allergen specific challenge test.

Atopic subjects may have simultaneously other allergies. Intermittent mild asthma, and mild and moderate persistent asthma are tolerated and treatment with inhaled steroids and other asthma medication is allowed. Atopic subjects may have additional skin symptoms. Quality of life, anxiety and patient history data is collected by questionnaires. All patients undergo a spirometry with a bronchodilator test, fractionale exhaled nitric oxide and a methacholine challenge before and a year after oral immunotherapy. Those with test results diagnostic for asthma (FEV1 response in a bronchodilator test  $> 12\% / 200\text{ml}$  and/ or PD $20 < 600 \mu\text{g/ml}$  methacholine in methacholine provocation test) (Crapo) are treated with asthma medication before hyposensibilisation treatment is started.

Exclusion criteria: adults with instabile cerebrovascular or heart disease, active autoimmune disease or cancer, or current use of betablocking agents. In addition, poorly controlled asthma or  $\text{FEV1} < 70\%$  ( $\text{FEV1} < -2\text{SD}$ ) are not tolerated.

#### **3.2. Allergen specific challenge test**

In egg allergy, increasing doses are given every 60 minutes during the egg or peanut allergen challenge. The protocol is done in a double-blind manner (day A, day B and one to seven days in between the two challenge days).

### **3.2.1. Food challenges.**

For milk allergy, increasing doses are given every 60 minutes (5 drops of milk, 1 ml of milk, 10 ml of milk, 50ml and 80 ml of milk). The challenge can be done as an open step-wise challenge during two days (Vlieg-Boerstra 2011).

The given doses in the peanut allergen challenge test are 5mg, 25mg, 50mg, 200mg and 1000mg of peanut protein. The 50mg of peanut protein is similar to  $\frac{1}{4}$  peanut. The maximum dose of 1000mg peanut protein is approximately 5 peanuts.

Accordingly, the challenge test in egg protein allergy is started with 5mg egg protein (150mg of meat ball) and then followed by 25mg of egg protein, 50mg, 500mg and 1000mg of egg protein.

The patient is followed for signs and symptoms of allergic reaction for two hours after the last dose of allergen. In the case of allergic reaction, the patient is treated with normal procedures: 0,5 mg epinephrine im in anaphylaxis, followed by corticosteroids (prednisolon 40mg po, methylprednisolon 40-80mg iv), cetirizin 10mg po and 0,9% NaCl iv, salbutamol and ipratropiumbromide as inhalation (Atrodual® 2,5ml)(Akuuttihoito-opas).

### **3.3. Study protocol**

In milk allergy, increasing doses are given using the following schedule. If the subject does not tolerate a given dose and symptoms are mild, then that dose or the previously tolerated one is repeated, and the protocol proceeds as outlined. If the subject experiences significant symptoms, then the protocol is stopped, and the highest tolerated dose is used as the starting daily one.

The schedule for oral immunotherapy against milk allergy:

Day no	Milk, diluted (1:10 drops)	Milk, dropps	Milk, ml
1	5		
7	10		
14	20		
21		5	
28		10	
35		20	
42			1
49			2
56			5

63	10
70	20
84	40
98	80
112	160
126	200

Similarly, in egg and peanut allergy, increasing doses are given using the predefined schedule. If the subject does not tolerate a given dose and symptoms are mild, then that

dose or the previously tolerated one is repeated, and the protocol proceeds as outlined. If the subject experiences significant symptoms, then the protocol is stopped, and the highest tolerated dose is used as the starting daily one.

Product	Week	Dose	Protein (mg)
Egg protein liquid 1mg/ml (vihreä)	1	0,1 ml	0,1
	2	0,2 ml	0,2
	3	0,4 ml	0,4
	4	1 ml	1
	6	2 ml	2
Egg protein	8 hoitaja	0,4 ml	4

liquid 10mg/ml (punainen)	10	0,8 ml	8
	12	1,2 ml	12
	14	2,5 ml	25
	16	5 ml	50
	18	10 ml	100
	20	20 ml	200
Egg protein	22	1 dose (spoon)	350
	24	2 dose	600
	26	3 dose	1050
	32	3 dose	1050

The schedule for oral immunotherapy against egg allergy:

The schedule for oral immunotherapy against peanut allergy:

Product	Week	Tea spoon or number/day (1 tl=2g)	Protein (mg)
Margarine contain peanut protein	1 vo	1 teaspoon	0,1
	2	2	0,2
	3	4	0,4
	4 vo	1	1
	6	2	2
	8	3	3
	10 vo	5	5
	12	6	6
	14 vo	1	10
	16	2,5	25
	18	5	50
Peanut	20 vo	¼ peanut	50
	22 vo	½	100
	24	¾	150
	26	1 peanut	200
	28 vo	1,5	300
	30	2	400
	32 vo	3 peanuts	600
	34	4	800

All the patients undergoing oral immunotherapy are prescribed with emergency medication such as antihistamine tablets, prednisolon tablets (40mg for three days in adults), epinephrine autoinjector (300 µg per dose) and salbutamol or terbutaline inhalator.

After escalating doses of allergen during the first phase of oral immunotherapy, the treatment is continued with the highest tolerated maintenance dose until one year of therapy. Spirometry with a bronchodilatator test, fractionale exhaled nitric oxide, a methacholine challenge and immunological parameters are studied a year after oral immunotherapy.

After one year of oral immunotherapy we have given the option to be followed further if the patient is willing to continue the immunotherapy. Spirometry with a bronchodilatator test, fractionale exhaled nitric oxide, and immunological parameters are studied once a year if the oral immunotherapy continues.

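### Egg schedule, week 24: two spoons are listed as 600 mg of protein, but the neighbouring rows make them 700 mg

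*Combined protocol and SAP*

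**What the plan says.** Section 3.3 (Study protocol) sets a fixed escalation for each allergen. For the two protein schedules, "in egg and peanut allergy, increasing doses are given using the predefined schedule". Each table gives a week, an amount to take and the protein in mg.

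- **Egg liquids, weeks 1 to 20.** Two products are named by strength. The first is headed "Egg protein liquid 1mg/ml (vihreä", and the second is a 10 mg/ml liquid with its own colour name.
- **Egg by the spoon, weeks 22 to 32.** One dose (a spoon) is 350 mg at week 22, two are 600 mg at week 24, and three are 1050 mg at weeks 26 and 32. No content per spoon is stated apart from these figures.
- **Peanut margarine, weeks 1 to 18.** The only product label is "Margarine contain peanut protein". The amount column is headed "Tea spoon or number/day (1 tl=2g", and no strength is given.

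Section 3.3 also says how reactions are handled. After mild symptoms, the same dose or the one tolerated before it is repeated. After significant symptoms, escalation stops and the highest tolerated dose becomes the daily dose. Maintenance up to one year uses the highest tolerated dose.

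**The concern.** The amount column and the protein column should be two descriptions of the same dose. At egg week 24 they are not. Someone who counts out two spoons and someone who measures 600 mg of protein would give different doses at the same step, and both would be following the table.

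These are escalation doses for adults with severe allergy. The week 24 dose can also become a patient's long-term dose: a patient who does not tolerate week 26 may stay at week 24. That patient's maintenance dose would then be uncertain by 100 mg, and could be reported as 600 mg when two spoons were taken.

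**Working it through.** **Inputs.** All come from the tables in section 3.3, except the peanut conversion in section 3.2.1.

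**1. Rows that do reproduce.** The formula is protein = amount × content per unit.

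- Egg liquid at 1 mg/ml: 0.1, 0.2, 0.4, 1 and 2 ml give 0.1, 0.2, 0.4, 1 and 2 mg. All 5 rows match.
- Egg liquid at 10 mg/ml: 0.4, 0.8, 1.2, 2.5, 5, 10 and 20 ml give 4, 8, 12, 25, 50, 100 and 200 mg. All 7 rows match.
- Whole peanut at 200 mg each: ¼, ½, ¾, 1, 1.5, 2, 3 and 4 peanuts give 50, 100, 150, 200, 300, 400, 600 and 800 mg. All 8 rows match. This agrees with section 3.2.1: "The maximum dose of 1000mg peanut protein is approximately 5 peanuts" (1000 / 5 = 200).

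The rows are exact, not rounded, so rounding is not a likely reason for a 100 mg gap.

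**2. Egg by the spoon.** Content per spoon = protein / number of spoons.

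| Week | Spoons | Stated mg | mg per spoon | At 350 mg per spoon | At 300 mg per spoon |
|---|---|---|---|---|---|
| 22 | 1 | 350 | 350 | 350 | 300 |
| 24 | 2 | 600 | 300 | 700 | 600 |
| 26, 32 | 3 | 1050 | 350 | 1050 | 900 |

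No single content fits every row. A content of 350 mg fits all rows except week 24. A content of 300 mg fits week 24 only.

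**3. Size.** At 350 mg per spoon, two spoons hold 2 × 350 = 700 mg. The gap is 700 − 600 = 100 mg. That is 100 / 600 = 17% of the stated dose, or 100 / 700 = 14% of the delivered dose. If 600 mg is the intended dose, the amount is 600 / 350 = 1.7 spoons.

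**4. Effect on the escalation steps.**

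- As printed: 600 / 350 = 1.71 and 1050 / 600 = 1.75.
- With 700 mg: 700 / 350 = 2.0 and 1050 / 700 = 1.5.

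The same schedule already has a 1.5-fold step (8 to 12 mg), many doublings (for example 25 to 50 to 100 to 200 mg) and a 2.5-fold step (0.4 to 1 mg). Both new ratios lie inside that range.

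**5. Peanut margarine.** Content per teaspoon = protein / teaspoons.

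- Weeks 1, 2, 3: 0.1/1, 0.2/2, 0.4/4 = 0.1 mg.
- Weeks 4, 6, 8, 10, 12: 1/1, 2/2, 3/3, 5/5, 6/6 = 1 mg.
- Weeks 14, 16, 18: 10/1, 25/2.5, 50/5 = 10 mg.

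Within each block the two columns agree exactly, and the spoon count restarts at 1 when the block changes. This is the pattern of three strengths in the ratio 1:10:100. At 2 g per teaspoon they are 0.05, 0.5 and 5 mg per gram. Stepping back from week 14 (1 teaspoon, 10 mg) to week 12 (6 teaspoons, 6 mg) therefore requires a change of product. With the week 14 product, 6 teaspoons would hold 6 × 10 = 60 mg.

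**The case against.** The egg slip is small. It affects one row, the resulting dose is still below the next step, and the weeks 26 and 32 target is consistent. The statistical consequence is small too: section 3.3.4 names tests only for IgE and methacholine results, so an error in tolerated dose could reach only the general descriptive summaries. All of this stands. It limits the weight of the point, but it does not reconcile the row.

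A reader might also infer that the peanut table contradicts itself, because one teaspoon is 0.1, 1 or 10 mg under one label. The documents do not support that. The label describes a kind of product and does not say that there is only one strength. The milligram column never falls, and either column leads to the same dose within a block. What is missing is a strength for each block. The layout of the product column is irregular (the 10 mg/ml egg label is split across two rows), so lost margarine labels cannot be excluded. A lost label would not explain the egg figure.

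**Conclusion.** The egg week 24 row is internally inconsistent, and nothing elsewhere in the document corrects it. If the spoon holds 350 mg, as the rows on both sides imply, the listed two spoons deliver 700 mg, which is 100 mg (17%) above the stated dose. The document does not show which column is wrong; 700 mg is the value consistent with the other rows.

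A reader might go further and conclude that patients were misdosed, that the trial's tolerated-dose data are wrong, or that staff or patients at home are exposed to tenfold errors. The documents support none of these. They report no misdosing and do not say that milligrams are recorded from this table. Home dosing is plausible from the daily amounts and the prescribed emergency medication, but section 3.3 does not state it. The tenfold or larger peanut figures describe a hypothetical use of the wrong product, not a conflict between stated doses. The sample size and the named tests are unaffected.

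**What to change.** In the egg table, make the week 24 amount and protein agree. Either change the protein figure to 700 mg or, if 600 mg is the intended dose, change the amount to about 1.7 spoons. The clinical team should confirm which, and confirm that the spoon holds 350 mg. Correct the matching dosing sheets.

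When reporting any patient whose highest tolerated dose is the week 24 step, use the corrected milligrams. If 600 mg turns out to be the intended dose but a patient actually took two spoons, report 700 mg for that patient.

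As a secondary labelling change, add the strength to each peanut margarine block: 0.1 mg per 2 g teaspoon in weeks 1–3, 1 mg in weeks 4–12 and 10 mg in weeks 14–18, once the team confirms these. State that a step back across a block needs a change of product.

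The cost is one corrected row, three strength labels and reissued dosing sheets. If 700 mg stands, the egg step sizes remain within the range that the schedule already uses.

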### **3.3. 3. Immunological parameters**

Serum samples are taken for allergen component evaluation. Egg white specific IgE and ovomucoid and ovalbumin specific IgE (Pharmacia Diagnostics AB, Uppsala, Sweden) before and after one year of oral immunotherapy for egg allergic patients. Casein,  $\alpha$ -lactalbumin and  $\beta$ 2-lactoglobulin specific IgE are studied for milk allergy before and after one year of immunotherapy. Similarly, IgE against peanut, Ara h 2, Ara h 3, Ara h 8, and Ara h 9 are studied in peanut allergy.

### **3.3. 4. Statistical methods**

Frequencies, means, medians, proportions and standard deviations are calculated for all the data. Pairwise IgE results, methacholine challenge test results are analyzed using the t-test or Wilcoxon signed rank test. The published reports on milk oral immunotherapy have been done in rather small number of study subjects, of which all have been children. The estimated numbers (50) of study subjects in this study tolerate also withdrawing of some of the subjects.

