## **4. Preliminary results since 2012**

### Milk allergy

Eight patients (62 %) have continued oral milk immunotherapy from 4 – 96 months with a mean of 23.5 months. Five (38 %) patients in total have discontinued the desensitization due to allergic reactions (4) or pregnancy (1). The dose range of oral immunotherapy at the current time point is from 3 ml (initiation phase) to 130ml (maintenance dose). Maximum dose has been 200ml. Six patients have reached the maintenance dose while two are still on the initiation phase. Overall milk and casein IgE levels have decreased in patients receiving the maintenance dose, indicating a possible decrease in immunologic reactions against the allergen.

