### Peanut allergy

In all peanut allergic patients, the Ara h2 level was increased before the immunotherapy with results ranging from 0.5-324 kU/l. The threshold for allergic symptoms in the challenge tests pre-OIT (oral immunotherapy) has varied from 5 to 50 mg. Oral immunotherapy has led to increased allergen tolerance by means of increasing the threshold for symptoms in our six adult patients. However, one patient had an anaphylactic reaction during OIT at the dose of 50 mg; at the initiation phase and the dose was given at hospital. This prompts careful patient selection and follow-up during OIT for adult patients.

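### Does leaving the scale and the choice between t-test and signed rank test open for skewed IgE put the IgE results at risk?

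*Combined protocol and SAP*

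**What the plan says.** Section 3.3.4 is the whole analysis plan for IgE. It describes the data by "Frequencies, means, medians, proportions and standard deviations are calculated for all the data", and then states: "Pairwise IgE results, methacholine challenge test results are analyzed using the t-test or Wilcoxon signed rank test". It names no scale, no rule for choosing between the tests, no significance level and no primary endpoint.

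The documents give two indications of how IgE is distributed. For the cited egg immunotherapy study, section 1 reports: "Mean baseline egg-specific IgE-level in the study was 24 kU/L (SD 44 kU/L) and 24-month level 12 kU/L (SD 19 kU/L". For the centre's own peanut patients, section 4 says that "the Ara h2 level was increased before the immunotherapy with results ranging from 0.5-324 kU/l".

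Two other places bear on the point. Section 3.1 includes "egg and milk allergen specific IgE antibodies" above 5.0 kU/l among the criteria that verify the milk diagnosis, so some patients are selected on a high baseline value. Section 3.3.3 lists the components to be measured, for example "IgE against peanut, Ara h 2, Ara h 3, Ara h 8, and Ara h 9 are studied in peanut allergy".

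**The concern.** A quantity that cannot be negative and has an SD of 1.6 to 1.8 times its mean is far from normal. The Ara h2 values span a 648-fold range (324 / 0.5). In a paired t-test on untransformed kU/l, a few patients with very high values dominate both the mean change and its standard error, so a consistent proportional fall in the others can go undetected. The wording permits that analysis.

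IgE is one of only two measures for which a test is named, and section 4 already reads falling milk and casein IgE as a possible sign of a weaker immune response. If the two permitted tests often disagree, an unstated choice could decide whether a fall is called significant. The tests also describe different quantities: a mean difference in kU/l, or a shift in the distribution of differences. A natural response is to require a t-test on log values, reported as a geometric mean ratio, with a rule for values below the assay limit.

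**Working it through.** **Inputs.** Baseline IgE 24 (SD 44) and later IgE 12 (SD 19) kU/L, from section 1. There are 30 patients per allergen (section 3.1). Retention is taken from section 4, where "Eight patients (62 %) have continued oral milk immunotherapy" and five stopped: 30 × 8/13 = 18.5, so 18 pairs. The documents give neither a significance level nor a before-after correlation. Two-sided 5% and a log correlation ρ of 0.5 to 0.9 are assumed. The plan states no power for IgE, and the 50 subjects in section 3.3.4 come without an effect size or SD, so there is no figure of the plan's own to reproduce.

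**Lognormal fit.** Log variance = ln(1 + (SD/mean)²).
- Baseline: ln(1 + (44/24)²) = ln 4.361 = 1.473, log SD 1.21; geometric mean 24/√4.361 = 11.5.
- Later: ln(1 + (19/12)²) = ln 3.507 = 1.255, log SD 1.12; geometric mean 12/√3.507 = 6.4.
- Ratio 6.4/11.5 = 0.56.

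**Check of one cell.** At ρ = 0.8 the SD of the log change is √(1.473 + 1.255 − 2 × 0.8 × 1.214 × 1.120) = 0.74. The standardised change is |ln 0.558|/0.74 = 0.79. With 18 pairs the noncentrality is 0.79 × √18 = 3.3, which agrees with the 88% below.

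**Power, 18 pairs (20,000 simulated trials per cell).** The signed rank test is applied to differences in kU/l.

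| ρ | t, untransformed | Signed rank | t, log scale | Signed rank minus untransformed t | Log t minus signed rank |
|---|---|---|---|---|---|
| 0.5 | 30% | 47% | 52% | 17 | 5 |
| 0.6 | 35% | 55% | 61% | 20 | 6 |
| 0.7 | 43% | 66% | 73% | 23 | 7 |
| 0.8 | 56% | 82% | 88% | 26 | 6 |
| 0.9 | 76% | 98% | 99% | 22 | 1 |

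Measured against a log-scale t-test, the untransformed t-test loses 22 to 32 points. Most of that is already recovered by the signed rank test that the plan names. With 30 pairs the untransformed t-test loses about 8 to 20 points to the signed rank test, and the log t-test gains 0 to 6 over it.

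**Disagreement between the permitted tests.** They differ at 5% in 21-29% of trials with 18 pairs. This is the power gap counted again: at ρ = 0.8 only the signed rank test is significant in 27.4% of trials and only the t-test in 1.2%, and 27.4 − 1.2 = 26.2 points is the difference in the table.

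**False positives from the open choice.** With no effect and no entry cut-off, calling the result significant if either permitted test is significant rejects in 5.4-6.4% of trials.

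**No effect, baseline required to exceed 5 kU/l.** Here regression to the mean looks like a fall.

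| Rule | 18 pairs | 30 pairs |
|---|---|---|
| Log t-test as main test | 6.6-14.4% | 7.9-22.0% |
| Better of the two permitted tests | 5.9-8.9% | 6.6-11.4% |

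Where the cut-off applies, fixing the log t-test as main test rejects more often under no effect than an unrestricted choice under the present text.

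**The case for a change.** The strongest case for a change is that the omission is certain and the remedy is a few sentences with no new data. The untransformed t-test loses power in every setting tried, though less outside the assumed correlations: against the log t-test the loss is 10 points at ρ = 0 and 15 at ρ = 0.95. That is a sound reason not to use the untransformed test. It does not show that an analyst facing these data would use it.

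The log scale can also matter more than the table suggests. With an assumed log SD of 1.6, a 40% fall, ρ = 0.8 and 18 pairs, the powers are 15%, 40% and 53%, so the log t-test gains about 12 points over the signed rank test. If the proportional change is independent of baseline (ratio 0.56, SD of log change 0.5 to 1.0), it gains about 5 to 29 points. This stands as a sensitivity. But that model implies a later log SD of √(1.473 + 0.25) = 1.31 to √(1.473 + 1.0) = 1.57, whereas the only pair of figures in the documents shows the log SD falling from 1.21 to 1.12. A signed rank test on log differences, which the wording equally allows, recovers nearly all of the gain: 82% against 84% at an SD of log change of 0.8.

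Finally, replacing values below an assay limit can move a geometric mean ratio. In one example with a true ratio of 0.56, three substitution rules gave 0.47, 0.65 and 0.74. That example assumes a limit of 0.35 kU/l and a component with a geometric mean of 0.5 kU/l. The documents state no assay limits and report no censored values, so the size of this effect in the trial cannot be judged from them.

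**Conclusion.** The plan does leave the scale and the choice of test open, and a t-test on untransformed kU/l would be a poor analysis: about 17 to 26 points less power than the permitted signed rank test with 18 pairs, and about 8 to 20 with 30. No change follows, for two reasons.

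First, this is missing detail that an analyst fills sensibly. Offering a t-test or a signed rank test conventionally means choosing by the shape of the data. The same section reports medians, and the skew is plain enough to lead to the signed rank test. Without the entry cut-off, the remaining freedom raises the false-positive rate by at most about 1.4 points (6.4 against 5).

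Second, the one concrete alternative is a trade-off. A log-scale t-test as main test gains 1 to 7 points over the signed rank test in the fitted setting, and more under other assumed models. In return it is more exposed to regression to the mean where the 5 kU/l criterion applied. That criterion is worded for the milk diagnosis and may not cover peanut or every component. In this uncontrolled before-after design a fall in IgE cannot be credited wholly to treatment, whichever of these tests is used.

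The figures are conditional. The means and SDs come from seven children at 24 months, whereas this trial studies adults at one year. The correlation and the 5% level are assumed. The 8 of 13 is continuation over 4 to 96 months in milk patients, not one-year completion, and up to 10 further milk patients may be added.

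### Section 3.3.4 puts the study at 50 subjects, but section 3.1 plans 100 and no combination of its groups gives 50

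*Combined protocol and SAP*

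**What the plan says.** Section 3.1 (Subjects) opens with "We study 100 subjects" and then lists four groups: (a) 30 adults with severe milk allergy, (b) 30 with severe peanut allergy, (c) 30 with severe egg allergy, and (d) up to 10 "patients whose oral immunotherapy against milk allergy has started as individually given treatment for clinical need".

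Section 3.3.4 (Statistical methods) names paired comparisons of IgE and of methacholine results, by t-test or Wilcoxon signed rank test. It then remarks: "The published reports on milk oral immunotherapy have been done in rather small number of study subjects, of which all have been children". The next sentence is the only one on sample size: "The estimated numbers (50) of study subjects in this study tolerate also withdrawing of some of the subjects". The section gives no significance level, power, effect size, standard deviation or expected withdrawal proportion.

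Section 3.3.3 (Immunological parameters) makes the IgE measurements specific to the allergen. Egg components are measured in egg-allergic patients. Casein and the other milk components "are studied for milk allergy before and after one year of immunotherapy". For the third allergen, "IgE against peanut, Ara h 2, Ara h 3, Ara h 8, and Ara h 9 are studied in peanut allergy".

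**The concern.** Both figures describe the size of the same study, and they differ by a factor of two. The figure in the statistics section also carries an argument: 50 is said to be enough to absorb some withdrawals. With no calculation beside it, that assurance has no other support. If the number is wrong, the assurance has been given for a study that section 3.1 does not describe.

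Withdrawal is a practical matter here. In the preliminary milk series in section 4, five patients (38%) stopped and eight continued. A reader who wants to know how many patients the paired comparisons start with, and how many could be lost, cannot get a consistent answer from the document.

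**Working it through.** **Inputs**
- Section 3.1: planned total 100; groups (a), (b) and (c) of 30 each; group (d) between 0 and 10.
- Section 3.3.4: 50 subjects, described as a number that tolerates withdrawals, so a number before losses.
- Section 4, milk: 8 continued and 5 discontinued, so 13 patients. Used only to test whether losses could explain the 50.

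**1. The total in section 3.1.** 30 + 30 + 30 + 10 = 100, so the stated total reproduces with group (d) full. With group (d) empty it is 90.

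**2. Can any set of groups give 50?** A sum of groups has the form 30k + d, where k is the number of full groups (0 to 3) and d runs from 0 to 10. Setting 30k + d = 50 gives d = 50 − 30k:
- k = 0 needs d = 50
- k = 1 needs d = 20
- k = 2 needs d = −10
- k = 3 needs d = −40

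None lies between 0 and 10. The attainable sums are 0–10, 30–40, 60–70 and 90–100. The nearest to 50 are 40 and 60.

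**3. Milk patients only.** The sentence before the 50 is about milk reports, so this reading deserves a check. Groups (a) and (d) give 30 + (0 to 10) = 30 to 40.

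**4. A number left after losses.** Reaching 50 would need a loss of 1 − 50/100 = 50% from 100, or 1 − 50/90 = 44% from 90. The preliminary milk proportion, 5/13 = 38%, would leave 100 × 8/13 = 62 or 90 × 8/13 = 55. The wording also places the 50 before withdrawals.

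**5. Size of the gap.** 50/100 = 50%; 50/90 = 56%.

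**6. Starting numbers for the named comparisons, if section 3.1 is current**

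| Comparison | Patients before withdrawals |
|---|---|
| Egg IgE | 30 |
| Peanut IgE | 30 |
| Milk IgE | 30, at most 40 with group (d) |
| Methacholine, if pooled across allergens | 90 to 100 |

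The upper figures assume that group (d) patients have measurements from before treatment. Section 3.1 asks for methacholine testing of all patients before treatment, and section 3.3.3 does not exclude group (d) from milk IgE. Neither says whether patients who had already started have a pre-treatment value.

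**The case against.** The best defence is that little depends on the 50. No analysis uses it, no power claim is attached to it, and it is called an estimate. This is a conflict between two sections, not a calculation gone wrong. All of that stands, and it limits the weight of the point. It does not reconcile the figures: an estimate can be loose, but section 3.1 fixes group sizes that cannot yield 50. The figure may have been carried over from an older protocol text or from the first part of the study. The documents do not say so, and that would explain the conflict without removing it.

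A reader might go further and infer that, because 50 exceeds the 30 patients per allergen, the plan overstates what each IgE comparison has, with a 20-patient shortfall. The documents do not support this. Section 3.3.4 attaches the 50 to the study as a whole, so subtracting a per-allergen 30 from it compares unlike quantities. Like for like, the direction reverses: 100 is more than 50, and an equal three-way split of 50 (an assumption) gives 50/3, about 17 per allergen, fewer than the 30 in section 3.1. Any comparison of detectable changes would also need a significance level and power that the plan does not state.

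Looking only at IgE would be one-sided as well. The methacholine comparison could use all 90 to 100 patients, and there the assurance about withdrawals becomes easier to support once the 50 is corrected.

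**Conclusion.** The point holds as an internal inconsistency in the stated sample size: 50 in section 3.3.4 against 90 to 100 in section 3.1. Neither a subset of groups, nor a milk-only reading, nor losses at the rate seen in the preliminary milk series accounts for the difference. It is more than a clerical matter because the plan's only statement on withdrawals depends on the number.

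The conclusion assumes that the group list in section 3.1 and the sentence in section 3.3.4 are both meant as current text. Nothing in the available text limits the 50 to a subset, and nothing shows which of the two totals is right. The documents do not establish that the study is too small, or that any one comparison is short of patients.

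**What to change.** The sponsor should confirm the current total and make sections 3.1 and 3.3.4 agree.

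- **If section 3.1 is current:** in section 3.3.4, replace the bracketed 50 with *up to 100 in total: 30 per allergen, plus up to 10 milk patients already on treatment*. Then make the withdrawal statement refer to the numbers analysed: 30 (milk at most 40) for each allergen-specific IgE comparison, and up to 90–100 for methacholine if pooled across allergens.
- **If 50 is current:** rewrite the total and the group sizes in section 3.1 so that they add up to 50.

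In the first case the cost is one or two sentences in section 3.3.4. In the second, the enrolment list must be redone. Neither case requires a power calculation to be revised, since the plan contains none.
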